## SOCIAL BEHAVIORAL INSTRUCTIONS AND TEMPLATE

NUMBER	DATE	PAGE
HRP-503a	12/21/2017	1 of 6

## Instructions and Notes:

- Depending on the nature of what you are doing, some sections may not be applicable to your research. If so, mark as "NA".
- When you write a protocol, keep an electronic copy. You will need a copy if it is necessary to make changes.

**1 Protocol Title**

Include the full protocol title: **Ecological Momentary Determinants of Sedentary Behavior**

**2 Background and Objectives**

Provide the scientific or scholarly background for, rationale for, and significance of the research based on the existing literature and how will it add to existing knowledge.

- Describe the purpose of the study.
- Describe any relevant preliminary data or case studies.
- Describe any past studies that are in conjunction to this study.

The unique attributes of sedentary behavior (SB) (e.g., ubiquitous, habitual, socially-reinforced) and its link to cardiometabolic health risk have led to several studies aimed at understanding the correlates of SB. However, these studies have primarily focused on "static" correlates (e.g., built environment, income status, educational attainment, etc.) and have largely ignored the complex situational, contextual, and dynamic "in the moment" factors that can influence SB.

The development of smart phone apps and wearable devices (e.g. Fitbit, apple watch, jawbone, etc.) within the technology industry has resulted in an increase in personal notifications to stand or move more during the workday. These prompts may vary in medium (phone, email, watch), delivery (textual, visual, sound, vibration) and content (personalized, generic, short, long, motivational, educational, feedback). However, the extent to which these prompts actually reduce SB is not fully understood.

The overall objective of this set of exploratory studies is to understand the personal, behavioral, environmental, and contextual factors that underpin SB and to systematically test a series of contextual prompt characteristics that may lead to subsequent change in SB.

The primary aims are:

**Aim 1.** Using Ecological Momentary Assessment (EMA), we will determine which personal (e.g. fatigue, mood, and stress level), behavioral (e.g. watching TV, working at desk, and eating meals), environmental (e.g. being at home or work, time of the day, and weather) and contextual factors are associated with SB. We will identify the combination of factors most likely to precede and proceed short (<30 min) and long (≥30 min) bouts of SB.

**Aim 2.** Using a micro-randomized screening experiment, we will identify efficacious behavioral strategies to produce an acute (within 5 min of receiving the prompt) reduction in SB based on three factors: (a) behavioral target (sit-to-stand vs. sit-to-light physical activities (LPA)); (b) social effects (group vs. individual); and (c) content (Target set vs. No target set). Our primary outcome will be a change from a sitting behavior to a standing behavior within 5 minutes of receiving the prompts. Furthermore, we will look at overall stand time (minutes), steps.

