## Inclusion criteria:

Full-time employees, males or females, ages 18-65, with sedentary working habits (as indicated by >7 hrs/day of sedentary time at work in the Sedentary Behavior Questionnaire), and are willing to engage in the study assessment and intervention for 10 weeks.

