**SOCIAL BEHAVIORAL INSTRUCTIONS AND TEMPLATE**

NUMBER	DATE	PAGE
HRP-503a	12/21/2017	3 of 6

This 10-week study has 2 main parts: (A) an EMA study and (B) a Screening experiment. Twenty participants will be recruited for the study.

Prior to the start of the study, participants will first have to complete an initial online screening survey to determine eligibility. All eligible participants will be requested to complete an online consent and depending on their smartphone operating system, will be sent instructions (see appendix D, E, F, and G) on how to download the smartphone apps that will be used in the study:

Smartphone App	OS	Description
PACO	Android or iOS	An open-source app designed that will be used to deliver EMA questions randomly throughout a participant's workday.
Daynamica	Android	An app designed to collect user activity and travel data using raw smartphone accelerometer and GOS data.
Prox	iOS	An iOS app designed to capture real-time indoor (office) location through proximity sensors deployed around the workplace.

Eligible and consented participants will be invited to a one-hour orientation session where they will be given detailed information about the study, along with answering any questions or concerns they may have. During this visit, proximity sensors will also be deployed to various key areas in the workplace (i.e., participant's desk, lobby, kitchen, and conference rooms).

Timeline:

	Week									
	Part A				Part B					
Measures	1	2	3	4	5	6	7	8	9	10
Main Survey	X						X			X
Daily logs	X	X	X	X			X	X	X	X
EMA	X	X	X	X						
Prompts							X	X	X	X
ActivPAL	X	X	X	X			X	X	X	X

Throughout Parts A and B (weeks 1-10):

All participants in both part A and B will be asked to complete daily logs that will ask them of the time they went to work and got off of work the previous day, sleep time of the previous night and the time they woke up, and any work-related meetings that they had the previous day. In addition, they will be asked to complete a battery of assessment (see appendix A for list of questionnaires) at three time points in the study: at week 1, 7, and 10. Participants will also be asked to wear the activPAL device on their thigh as an objective measure of sedentary and physical activities. They will be asked to wear the device continuously throughout the study except for the interview weeks (week 5 and 6). The activPAL will be dropped off every Monday morning and picked up every Friday of the same week.

Part A (Weeks 1-4):

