**SOCIAL BEHAVIORAL INSTRUCTIONS AND TEMPLATE**

NUMBER	DATE	PAGE
HRP-503a	12/21/2017	4 of 6

Participants will receive 3 random EMAs (Appendix B) per day throughout the 4-week study. EMAs will only be sent during work hours (9AM-5PM). A total of 1200 EMA observations (3x/day x 20 work days x 20 participants) will be collected.

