## **Statistical analyses**

### *PART A*

All statistical analyses will be completed using SAS Version 7.1 (SAS Institute, Inc., Cary, North Carolina). Mixed model analyses will be conducted using PROC MIXED to examine the bi-directional associations of sitting, standing, and moving behaviors and affective states. All models will be adjusted for age, gender, race and job type.

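### Aim 1 asks what precedes and follows sitting bouts, but most random-time EMAs will fall mid-bout and SAP Part A does not adjust for sitting already done

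*Protocol*

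**What the plan says.** Protocol section 2, Aim 1, sets out to find "the combination of factors most likely to precede and proceed short" and long bouts. The full pair of classes is "short (<30 min) and long (≥30 min) bouts of SB", so they are defined by bout length. Personal states (fatigue, mood, stress) are named among the candidate factors, alongside behavioral and environmental ones such as weather.

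The sampling is in section 7, Part A: "Participants will receive 3 random EMAs (Appendix B) per day throughout the 4-week study", between 9AM and 5PM. Nothing ties an EMA to the start or end of a bout. The planned yield is stated: "A total of 1200 EMA observations (3x/day x 20 work days x 20 participants) will be collected".

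Eligibility (section 4) requires sedentary working habits, "as indicated by >7 hrs/day of sedentary time at work in the Sedentary Behavior Questionnaire". Posture is recorded by device in weeks 1-4: "Participants will also be asked to wear the activPAL device on their thigh as an objective measure of sedentary and physical activities".

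SAP Part A plans mixed models "to examine the bi-directional associations of sitting, standing, and moving behaviors and affective states", with age, gender, race and job type as the covariates. It names no bout outcome, no 30-minute class, no rule linking an EMA to a bout and no term for prior sitting. SAP Part B, by contrast, does adjust for sitting in the 30 minutes before a prompt.

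**The concern.** A rating given in the middle of a bout comes after part of that bout and before the rest of it. It cannot show what came before the bout or what came after it. Minutes already sat may also be linked to both sides of the association. They can change the rated state, and, unless bouts are memoryless, they predict how much longer the person will sit. A forward-looking model without that term mixes the effect of sitting on the state with the effect of the state on sitting.

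The precede half of Aim 1 exists to separate these two directions. If it fails, the study could report fatigue or stress as a trigger of prolonged sitting when it is a consequence. More observations would not cure this, because the error is systematic.

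**Working it through.** **Planned count.** 3 per day x 20 work days x 20 participants = 1200, which reproduces the protocol's figure. The documents give no bout-length, bout-count or power figure for Aim 1.

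**Share falling mid-bout.** Taking the self-reported 7 h at face value in an 8-hour window, 7/8 = 87.5%, and 1200 x 0.875 = 1050 EMAs during sitting, leaving about 150. If the true share were only 65% (an assumption), 1200 x 0.65 = 780 during sitting and 420 not.

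**Over-sampling of long bouts.** A random time hits a bout with probability proportional to its length. For exponential bouts of mean m (assumed), the share of all bouts lasting 30 min or more is exp(-30/m). Among bouts hit by an EMA it is (1 + 30/m) x exp(-30/m).

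| m (min) | All bouts | Bouts hit |
|---|---|---|
| 15 | 14% | 41% |
| 20 | 22% | 56% |
| 30 | 37% | 74% |

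This alone does little to the odds ratio of a factor fixed at bout start. Comparing assumed means without and with the factor, 20 vs 40 min moves it from 3.12 to 3.78 (3.78/3.12 = 1.21, or +21%), and 10 vs 20 min moves it from 5.48 to 5.07 (5.07/5.48 = 0.93, or -7%). Those are the extremes of the cases tried.

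**Elapsed sitting.** With m = 20, mean minutes already sat at the EMA are about 29 in long bouts and 9 in short ones. Suppose the rating has no effect on later sitting, but P(high rating) = expit(-0.7 + 0.02 x minutes already sat). Both coefficients are assumed. A hand check for total-length classing is 0.02 x (29 - 9) = 0.4, and exp(0.4) = 1.49, a false odds ratio of about 1.5.

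**Simulation with that rating model, true odds ratio 1.0.** The outcome is 30 min or more versus less. Ranges span several runs.

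| Assumed bouts | Current bout by total length | Remaining time, unadjusted | Remaining time, adjusted for elapsed minutes |
|---|---|---|---|
| Exponential, mean 15-30 min | 1.4-1.7 | 0.97-1.03 | about 1.0 |
| Lognormal, sigma 1, median 8-20 min, capped at 240 min | 1.7-2.0 | 1.25-1.35 | 1.00-1.06 |
| Exponential with means varying (log-SD 0.5) | 1.6-2.1 | 1.16-1.21 | 1.00-1.06 |

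The exponential row is clean without adjustment only because exponential bouts are memoryless: remaining time is independent of elapsed time by construction. In the other two rows elapsed time predicts remaining time, so the adjustment is what removes the false association.

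**The case against.** The strongest reply is that the SAP plans no analysis by total bout length. Part A relates posture and movement to affect, and its bi-directional wording is compatible with looking at sitting before and after each EMA. A random EMA does precede later sitting and follow earlier sitting. This stands. A reader might infer from the 30-minute classes that the study will report odds ratios inflated to 1.4-2.1, but no section assigns an EMA to the bout in progress or classes it by total length. Those figures describe what would happen if an analyst took that route, and nothing in the SAP steers away from it.

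A reader might also infer that length-biased sampling is the main fault, or that Aim 1 cannot be answered. Neither follows. Length bias alone moved odds ratios by -7% to +21%, and the activPAL record allows a well-ordered analysis.

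It is also fair to say that the drift is assumed, that factors such as weather cannot be changed by sitting, and that the protocol calls the studies exploratory. The first two limit the scope and size. The third does not help, because an exploratory result with the direction reversed still misleads.

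What the reply does not meet is the covariate list. A forward-looking Part A model run as written has no term for sitting already done.

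**Conclusion.** The point holds in limited form. Most EMAs will fall during sitting, so they cannot speak to what precedes or follows a whole bout, and Part A gives no bout analysis in its place. Any Part A model of later sitting that uses only the stated covariates is open to confounding by elapsed sitting, for states that change while sitting.

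Under the assumed drift, the false odds ratio for remaining sitting time is about 1.2-1.3 when bouts are not exponential, and about 1.0-1.06 after adjustment. If bouts were exponential, or if the state did not change with sitting, this bias would be absent. The mid-bout share rests on self-reported sitting and an 8-hour day; at an assumed 65% it is still the majority. The size in this study is unknown because the documents give neither bout lengths nor drift.

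**What to change.** In SAP Part A:

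- Add activPAL minutes already sat at the EMA, in a flexible form such as a spline, as a covariate in every model of later sitting. Part B already applies the same principle with prior sitting.
- For EMAs answered while sitting, use sitting time remaining after the EMA as the precede outcome, always with that adjustment, and minutes already sat as the follow exposure. Do not class these EMAs by the total length of the current bout.
- For EMAs answered while not sitting, use the next bout to start (precede) and the last bout to end (follow), and keep the whole-bout classes of under 30 and 30 or more minutes for these.

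Reword Aim 1 to say that results from mid-bout EMAs concern remaining or elapsed sitting, not whole-bout length.

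The cost is two derived activPAL variables and some text, with no new data collection. The real downside is a change of estimand for most EMAs: a 50-minute bout sampled at minute 25 has 25 minutes remaining and counts as short on that outcome. The whole-bout question then rests on the minority of EMAs answered while not sitting, about 150 to 420 of the 1200 under the shares used above.

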**3 Data Use**

Describe how the data will be used. Examples include:

- Dissertation, Thesis, Undergraduate honors project
- Publication/journal article, conferences/presentations
- Results released to agency or organization
- Results released to participants/parents
- Results released to employer or school
- Other (describe)

Data will be used for publications and conference presentations.

## SOCIAL BEHAVIORAL INSTRUCTIONS AND TEMPLATE

NUMBER	DATE	PAGE
HRP-503a	12/21/2017	2 of 6

## 4 Inclusion and Exclusion Criteria

Describe the criteria that define who will be included or excluded in your final study sample. If you are conducting data analysis only describe what is included in the dataset you propose to use.

Indicate specifically whether you will target or exclude each of the following special populations:

- Minors (individuals who are under the age of 18)
- Adults who are unable to consent
- Pregnant women
- Prisoners
- Native Americans
- Undocumented individuals

## Inclusion criteria:

Full-time employees, males or females, ages 18-65, with sedentary working habits (as indicated by >7 hrs/day of sedentary time at work in the Sedentary Behavior Questionnaire), and are willing to engage in the study assessment and intervention for 10 weeks.

## Exclusion criteria:

Non-ambulatory, pregnant, non-English speaking, diagnosis of psychiatric problems or taking psychiatric medications, and a medical history that prohibits prolonged standing.

## 5 Number of Participants

Indicate the total number of participants to be recruited and enrolled: 20

## 6 Recruitment Methods

- Describe who will be doing the recruitment of participants.
- Describe when, where, and how potential participants will be identified and recruited.
- Describe and attach materials that will be used to recruit participants (attach documents or recruitment script with the application).

Participants will be employees of the Parking and Transit Services (PTS) at ASU, recruited in person by members of the research team. We have already established contact with PTS and they have expressed their support to this project (see supplemental document for letter of support).

## 7 Procedures Involved

Describe all research procedures being performed, who will facilitate the procedures, and when they will be performed. Describe procedures including:

- The duration of time participants will spend in each research activity.
- The period or span of time for the collection of data, and any long term follow up.
- Surveys or questionnaires that will be administered (Attach all surveys, interview questions, scripts, data collection forms, and instructions for participants to the online application).
- Interventions and sessions (Attach supplemental materials to the online application).
- Lab procedures and tests and related instructions to participants.
- Video or audio recordings of participants.
- Previously collected data sets that will be analyzed and identify the data source (Attach data use agreement(s) to the online application).

**SOCIAL BEHAVIORAL INSTRUCTIONS AND TEMPLATE**

NUMBER	DATE	PAGE
HRP-503a	12/21/2017	3 of 6

This 10-week study has 2 main parts: (A) an EMA study and (B) a Screening experiment. Twenty participants will be recruited for the study.

Prior to the start of the study, participants will first have to complete an initial online screening survey to determine eligibility. All eligible participants will be requested to complete an online consent and depending on their smartphone operating system, will be sent instructions (see appendix D, E, F, and G) on how to download the smartphone apps that will be used in the study:

Smartphone App	OS	Description
PACO	Android or iOS	An open-source app designed that will be used to deliver EMA questions randomly throughout a participant's workday.
Daynamica	Android	An app designed to collect user activity and travel data using raw smartphone accelerometer and GOS data.
Prox	iOS	An iOS app designed to capture real-time indoor (office) location through proximity sensors deployed around the workplace.

Eligible and consented participants will be invited to a one-hour orientation session where they will be given detailed information about the study, along with answering any questions or concerns they may have. During this visit, proximity sensors will also be deployed to various key areas in the workplace (i.e., participant's desk, lobby, kitchen, and conference rooms).

Timeline:

	Week									
	Part A				Part B					
Measures	1	2	3	4	5	6	7	8	9	10
Main Survey	X						X			X
Daily logs	X	X	X	X			X	X	X	X
EMA	X	X	X	X						
Prompts							X	X	X	X
ActivPAL	X	X	X	X			X	X	X	X

Throughout Parts A and B (weeks 1-10):

All participants in both part A and B will be asked to complete daily logs that will ask them of the time they went to work and got off of work the previous day, sleep time of the previous night and the time they woke up, and any work-related meetings that they had the previous day. In addition, they will be asked to complete a battery of assessment (see appendix A for list of questionnaires) at three time points in the study: at week 1, 7, and 10. Participants will also be asked to wear the activPAL device on their thigh as an objective measure of sedentary and physical activities. They will be asked to wear the device continuously throughout the study except for the interview weeks (week 5 and 6). The activPAL will be dropped off every Monday morning and picked up every Friday of the same week.

Part A (Weeks 1-4):

For part one, all eligible participants will be asked to download a mobile app, pre-programmed to collect ecological constructs. Proper instructions on how to use this app and what to expect in the following weeks will be given and any questions from the participants will be addressed (15 mins).

**SOCIAL BEHAVIORAL INSTRUCTIONS AND TEMPLATE**

NUMBER	DATE	PAGE
HRP-503a	12/21/2017	4 of 6

Participants will receive 3 random EMAs (Appendix B) per day throughout the 4-week study. EMAs will only be sent during work hours (9AM-5PM). A total of 1200 EMA observations (3x/day x 20 work days x 20 participants) will be collected.

**Part B (weeks 5-9):**

Participants will be randomized to either receive or not to receive prompts every work hour (8 per day) via email, for 4 weeks. A total of 80 prompts will be sent to participants over a 4-week period during their work hours (9AM-5PM) on workdays.

**8 Compensation or Credit**

- Describe the amount and timing of any compensation or credit to participants.
- Identify the source of the funds to compensate participants
- Justify that the amount given to participants is reasonable.
- If participants are receiving course credit for participating in research, alternative assignments need to be put in place to avoid coercion.

For part A of the study, participants who complete the entire 4-week will receive a \$20 gift card as compensation for their time and effort. In addition, participants will receive an additional \$10 for completing at least 80% of the EMA questionnaires for that 2-week period (24 out of 30 EMAs), for up to \$20 of additional compensation for the entire 4 weeks of part A. For part B of the study, all participants who complete part B will be compensated with a \$20 gift card. Furthermore, participants will also receive feedback on their physical activity behaviors gleaned from the activPAL device.

**9 Risk to Participants**

List the reasonably foreseeable risks, discomforts, or inconveniences related to participation in the research. Consider physical, psychological, social, legal, and economic risks.

The proposed study presents no major risk for physical injury and does not involve any invasive procedures. However, minor complications could still potentially arise:

- Potential risks to participants include possible physical discomfort that may occur due to participation in a program focused specifically on increasing walking/reducing sitting time at the workplace, although standing/walking behaviors are totally voluntary.
- Participation in the study may cause some participant burden from the assessment questionnaires and prompts designed to reduce sedentary activity that they will be receiving multiple times per day (3/day). As these text messages will be sent randomly throughout the study period, it can cause disruption in the normal daily activities of the participants. However, these questionnaires are designed to be short (<1 min to complete) and easy to answer.
- Any collected data (demographic information, answers to questionnaires, etc.) will be at risk for divulgence. Each participant will be assigned a participant ID number immediately after enrollment. All collected data will be stored a secure ASU storage drive, which is only accessible to the researcher.

**10 Potential Benefits to Participants**

Realistically describe the potential benefits that individual participants may experience from taking part in the research. Indicate if there is no direct benefit. Do **not** include benefits to society or others.

While no benefits to the participants in the study can be guaranteed, it is possible that participating in the study will help the individuals to be aware of their physical activity behavior and develop strategies to decrease their sedentary behavior at the workplace.

